The intervention will be a structured in-depth interview with a patient with a chronic illness that has been chosen by the student's allocated GP teacher. These chronic diseases are the four conditions at the top of a list of diseases with high disability-adjusted life years (DALY) scores in Switzerland: ischemic heart disease, low back pain, major depressive disorder and COPD [21]. GP teachers who only see children are asked to choose a patient who has a chronic cardiac condition, a chronic lung disease, or another chronic illness that has a significant effect on the child's quality of life, the interview to be carried out at the child's home with one or both parents, and the child if she/he is old enough to take part in the interview.

GP teachers and students will be told that the students' intervention interviews need to be unaccompanied and at patients' own homes, but in justified, exceptional cases, and after consultation with a member of the research team, the interview may take place in the GP teacher's practice premises. The interview will be followed by a structured interview with the practice nurse and then a structured debriefing interview with the GP teacher.

Sham comparator

In the sham comparator, the student's the allocated GP teacher will give the student time to read a document that gives information about consultation skills, and asks questions that the student will need to discuss with the GP teacher. The document is designed to have real educational value, and to complement BIHAM's department-based consultation skills teaching. The use of this approach as the sham intervention is based on a study that found that a behavioural science course (including consultation skills teaching) had no effect on students' PPOS scores [19].

Data collection

At the start of the academic year (i.e. before the interventions), students will complete a SurveyMonkey questionnaire that asks for demographic information (gender, history of serious chronic illness in the participant, a friend or close relative, history of training or patient contact other than in medical school) and the PPOS D12 form.

At the end of their GP attachment (i.e. after the interventions), students will complete a SurveyMonkey questionnaire that asks whether they had the intervention or sham comparator or neither (and if neither, why), and the PPOS D12 form. Consent to use these data for research will also be requested.

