Following this, RF conducted a focus group interview with the participating students. The discussion was recorded and transcribed in full. [name] and MH analysed parts of each the transcript independently, then independently developed a coding frame. Their coding and thematic analysis was similar. The findings (the experiences, suggestions and criticisms of the piloting students) were used to make improvements in the organisation and in the information sheets for patients, students, MPAs and GPs.

Three medical students then piloted the re-designed interview pro-forma with one of the researchers ([name]) role-playing the patient), and they gave feedback with recommendations on how the pro-forma could be further improved. Following this, RF, [name] and MH reviewed the pro-forma and designed the final version. The interview proforma and instructions on implementation of the intervention will be sent to students and their GP teachers before the students' final visits to their teaching practices.

Development of the sham comparator

MH wrote an English-language 'Communication skills for BIHAM medical students' didactic document, which included sections on 'Why should I learn about communication skills?', 'What do patients want from a doctor?', 'What information are patients looking for?', 'What consultation skills should I use when I interview patients?', 'Do good communication skills really matter?', 'How can I learn good interpersonal and consultation skills?', 'How is a good consultation structured?', and 'Questions to discuss with your GP teacher'. This document was translated into German by [name]. The resulting 1,850-word, 9-page document and instructions on implementation of the intervention will be sent to students and their GP teachers before the students' final visits to their teaching practices.

Randomisation

Participants will be allocated to intervention or sham intervention through random sequences generated in the SPSS statistical package.

Blinding procedures

This study will be partially blinded:

- Screening and enrolment. A person blinded to the purpose of the interventions (i.e. that one is the intervention, the other is a sham comparator) will enrol participants and allocate them to their arm of the study. This person will work separately from the rest of the trial team and all team members will be asked to sign a form stating that they will not disclose the purpose of the interventions to this person.

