- Students. In a tailored informed consent procedure, students will be given a 'high-level description' of the study objectives with only superficial information on the study interventions, as accepted by ethics committees in similar studies. They will be informed that they are randomised to one of two study groups, without revealing that one is an intervention and the other is a sham comparator. The aim of this is to minimise performance and other reporting biases.
- GP teachers. A similar approach will be taken with information for the GP teachers, so that they also have only a 'high-level' description of the study objectives.

Statistical analysis

Descriptive statistics will be used to describe the relationships between student demographics and PPOS scores. Mean pre- and post-test PPOS scores will be compared using paired *t* tests. Differences between PPOS scores in the intervention and control groups will be examined with unpaired *t* tests. For the nested study, GPs' PPOS scores and changes in their students' PPOS scores will be compared using paired *t* tests.

The sample size calculation for the primary outcome was based on reported mean reduction of 0.11 in the PPOS score over one year in a group without any intervention [20], and a mean increase of 0.05 in the intervention group. We therefore assumed a mean difference 0.16, with a standard deviation of 0.42. The study was designed with a 5% level of significance and a 90% power to reject the null hypothesis of equivalence between the two groups. To achieve this objective, 220 students would be required (110 for each group). Assuming a 20% drop-out, we therefore aimed to enrol a total of 275 students.

Discussion

This research will consider the effect of an in-depth, structured interview with a patient with a chronic illness on changes in first-year medical students' levels of patient-centredness. There is existing evidence that medical students' levels of patient-centredness reduce over their student years, and this study will contribute to an understanding of how this reduction can be minimised or reversed.

Strengths

To our knowledge, this is the first randomised controlled trial that has been designed to study the effect of an intervention on medical students' levels of patient-centredness. The intervention materials were carefully developed and piloted by GP teachers and medical students, and therefore grounded in their clinical and educational experience.

Limitations

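### Does the end-of-attachment questionnaire reveal to students that one of the two activities is a sham?

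*Combined protocol and SAP*

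**What the plan says.** The Data collection section of the protocol describes two student questionnaires. The one at the start of the academic year "asks for demographic information (gender, history of serious chronic illness in the participant" and other background items, together with the PPOS-D12. The one at the end of the attachment "asks whether they had the intervention or sham comparator or neither (and if neither, why), and the PPOS D12 form".

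Blinding procedures opens with "This study will be partially blinded". Students receive only a general description of the objectives and learn that there are two groups, "without revealing that one is an intervention and the other is a sham comparator". The reason follows: "The aim of this is to minimise performance and other reporting biases". The person who enrols and allocates students is also kept unaware, and is described as "A person blinded to the purpose of the interventions (i.e. that one is the intervention, the other is a sham comparator". Team members sign an undertaking not to tell that person.

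The protocol does not print the on-screen text of the question about the activity, nor its position relative to the PPOS-D12. Appendix 1 gives only the 12 PPOS-D12 statements and their response options.

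**The concern.** The two labels that Blinding procedures withholds from students are the two labels that Data collection uses for a question put to every student. The protocol treats this pair of labels as the thing to be concealed, since it defines the purpose hidden from the enroller in the same terms.

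The place is sensitive. The primary outcome is a self-reported attitude score, and its follow-up value is collected on the same form. If the labels appeared before or beside the PPOS-D12, concealment would end at the moment of measurement. The baseline form as described has no such item, so any reaction would enter the follow-up score alone. A reaction that differed between arms would bias the randomised comparison. A reaction common to both would still distort the within-group analysis ("Mean pre- and post-test PPOS scores will be compared using paired" *t* tests).

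**Working it through.** No figure in the plan depends on this point, so the check is mainly a comparison of texts. A short calculation shows what would be exposed.

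**1. Exposure if the labels were shown first.** Inputs from Statistical analysis: 275 enrolled, 20% drop-out. Planned completers: 275 × (1 − 0.20) = 220, or 110 per group, as the protocol states. The item is on 1 of the 2 student questionnaires. At most, 220 follow-up scores and no baseline scores could be touched.

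**2. How a reaction would enter the analyses.** Let r_I and r_S be the mean shift in the follow-up score caused by seeing the labels, in the interview and reading groups.
- Between-group difference in change = true difference + (r_I − r_S).
- Within-group change = true change + r_I (or r_S).

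If r_I = r_S, the randomised comparison is unaffected and only the paired tests shift. If the labels are never shown, r_I = r_S = 0 and neither analysis is affected. The documents give no value for either term. Everything therefore turns on whether the labels are shown.

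**3. Does the text show that they are?**
- *Type of sentence.* Data collection summarises the content of each form. The baseline items are given in the same summary style, and no item is reproduced.
- *Language.* The protocol's title page marks it as English only. The PPOS-D12 is a German instrument, Appendix 1 is headed as an English translation, and the sham document was translated into German. The survey language is not stated. If it is German, the English phrase cannot be the on-screen text.
- *Use of the labels.* Development of the sham comparator says the reading document is sent with instructions on implementing the intervention, the same term used for the interview materials. Data collection uses the plural, interventions, for both arms. The word is authors' shorthand and is weak evidence of what a student sees.
- *Answerability.* The question is there to record what each student did. A student who has not been told which activity is the sham could only guess at an answer in those terms. To serve its purpose, the item has to name the activity.
- *The specific rule.* Blinding procedures states directly what students may learn. A general description elsewhere is properly read subject to it, and the two sections then agree without altering either.

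**4. What a neutral item discloses.** Every student knows whether they interviewed a patient or read a document. Asking which it was adds no information about purpose.

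**5. Gain from further safeguards.** With neutral wording, nothing in the documents shows a benefit from fixing the item order, using separate pages or blocking back-navigation. Nor is the survey needed to identify interviews moved from the home. The Intervention section says that "the interview may take place in the GP teacher's practice premises" only in justified exceptions and after consulting the research team, who would therefore know of them.

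**The case for a change.** The strongest contrary case is that a reader cannot confirm concealment from the documents. The protocol takes formal steps to keep the labels from one enroller, yet states no matching safeguard for a question that goes to every student. The Limitations section admits that participants may guess the researchers' intentions, but being told by the trial's own form is a different and avoidable route. The outcome could also be sensitive. If the score is the mean of 12 items in one-point steps (an assumption; the protocol does not give the scoring), the planned difference of 0.16 equals 0.16 × 12 = 1.92 item-steps. A between-arm shift of one step on about two items would then match the whole target effect. Neutral wording costs almost nothing.

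Part of this stands. The wording and order are not written down, and the phrase in Data collection is careless beside Blinding procedures. The sensitivity figure, however, says how little shift would matter, not that any shift occurs. The safeguard said to be missing is the student rule in Blinding procedures, which already covers anything shown to students. The low cost of neutral wording also makes it likely that whoever builds the survey will use it.

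**Conclusion.** The concern does not call for a change. What remains is an unprinted survey item whose sensible wording follows from the plan's own blinding rule. No contradiction in what students are shown is demonstrated, and no bias in the primary comparison is demonstrated or can be estimated. The sample size, the outcome and the tests are all untouched.

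This rests on one assumption: that the item names the activity (patient interview, reading and discussing the document, or neither and why) and not its role in the trial. If the live survey did show the labels before the PPOS-D12, up to 220 follow-up scores would be exposed and the conclusion would need revisiting. The documents give no reason to expect that.

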This research receives no specific grant from any funding agency in the public, commercial or not-for-profit sectors.

Availability of data and materials

Only the research team at the University of Bern will have access to the data during the study. The datasets analysed during this study will be available from the corresponding author on reasonable request.

Ethics approval and consent to participate

The research proposal was presented to the regional ethics committee (Kantonale Ethikkommission für die Forschung, Gesundheits- und Fürsorgedirektion des Kantons Bern) and a waiver was issued on Jan 24th 2018 stating that the study does not fall under the Swiss Human Research Act (BASEC-Nr. Req-2018-00059).

Students and GP teachers will be sent an email with a link to the online survey, where they will be given information about the project, an assurance that their answers are confidential, and a request for their agreement to allow their data to be used in the study. Clicking on the 'agreement' button will be considered as consent to participate in the study. Student and their GP teachers, as well as the selected patients in the intervention group, will be given information sheets about the study.

Competing interests

The authors declare that they have no competing interests.

Timetable

| | Sep-Dec 17 | Jan 18 | Feb 18 | Mar-May 18 | Jun 18 | Jul 18 | Aug 18 | Sep 18 | Oct 18- May 19 | May- July 19 | Aug- Sept 19 |
|----------------------|---------------|-----------|-----------|---------------|-----------|-----------|-----------|-----------|-------------------------|--------------------|--------------------|
| Pilot 1 | | | | | | | | | | | |
| Ethics application | | | | | | | | | | | |
| Pilot 1 analysis | | | | | | | | | | | |
| Protocol | | | | | | | | | | | |
| Pilot 2 and analysis | | | | | | | | | | | |
| Finalise materials | | | | | | | | | | | |
| Data collection | | | | | | | | | | | |
| Write report | | | | | | | | | | | |
| Write paper | | | | | | | | | | | |

References

1. Medical Protection Society. Medical Professionalism - What do we mean? London2017 [31 October 2017]. Available from: <http://www.medicalprotection.org/uk/advice-booklets/professionalism-an-mps-guide/chapter-1-medical-professionalism-what-do-we-mean>

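### The only dated request for students' consent to data use comes after the intervention, so a choice made after exposure can decide who enters the primary analysis

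*Combined protocol and SAP*

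**What the plan says.** The Data collection section describes two student questionnaires. For the first: "At the start of the academic year (i.e. before the interventions), students will complete a SurveyMonkey questionnaire that asks for demographic information" and the PPOS-D12; no consent item is listed. For the second: "At the end of their GP attachment (i.e. after the interventions), students will complete a SurveyMonkey questionnaire". That one asks which activity the student had, or neither and why, and repeats the PPOS-D12. The description ends: "Consent to use these data for research will also be requested".

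Three other places bear on when students agree:

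- Blinding procedures, Screening and enrolment: a blinded person "will enrol participants and allocate them to their arm of the study". Consent is not mentioned.
- Blinding procedures, Students: "In a tailored informed consent procedure, students will be given a" high-level account of the objectives. They learn that they are randomised, "without revealing that one is an intervention and the other is a sham comparator". No date is given.
- Ethics approval and consent to participate: an e-mailed link leads to an online survey containing "a request for their agreement to allow their data to be used in the study". Which of the two surveys is meant is not stated.

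The primary outcome is the change in PPOS-D12 from baseline to the end of the attachment. On the comparison, the Statistical analysis section says: "Differences between PPOS scores in the intervention and control groups will be examined with unpaired" t tests. It defines no analysis set and does not say that students are compared by randomised arm.

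**The concern.** A randomised comparison is protected when membership of the analysed groups is settled before allocation, or at least does not depend on it. Here the one data-use request with a date falls after allocation and exposure, in the same questionnaire in which students report what they did. They are not told which activity is the sham, but a home interview with a patient and a reading document are easy to tell apart.

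Students put off by the interview might decline, or students bored by the reading might. If those who decline also differ in how their attitudes changed, the difference between consenting students is no longer an estimate of the randomised effect. The bias could go either way. It could not be reliably corrected afterwards, because the data of those who decline may not be used.

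**Working it through.** **Reading the passages together.** Four places touch on student enrolment or agreement, and only Data collection ties a data-use request to a time, which is after the interventions. The agreement button in the Ethics section serves the same purpose (use of data) but has no date. An earlier agreement to take part would not remove the later request, and the plan does not say what happens to a student who agrees early and declines late. Whether the late request covers only the final questionnaire or both, refusal removes the change score, which needs both.

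**Size of the possible bias.** The plan gives no figure for this, so there is none to reproduce. What follows is an illustration.

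Inputs from the Statistical analysis section: assumed difference 0.16, SD 0.42, 110 students per arm. Assumed inputs, not in the documents: the refusal rate r in each arm, and the gap g, which is mean change in consenters minus mean change in refusers.

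In one arm, the overall mean = (1 − r) × consenters' mean + r × refusers' mean, so the consenters' mean = overall mean + r × g. The bias in the between-arm difference is therefore r₁g₁ − r₀g₀. With the same gap in both arms this is (r₁ − r₀) × g.

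Standard error = 0.42 × √(2/110) = 0.0566. The last column is the probability of p < 0.05 when there is no true effect (two-sided t test, 218 degrees of freedom, noncentral t with noncentrality bias/0.0566).

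| Case | Refusal by arm | Gap | Bias | Share of 0.16 | Chance of p < 0.05 |
|---|---|---|---|---|---|
| Low | 10% vs 5% | 0.25 SD = 0.105 | 0.05 × 0.105 = 0.00525 | 3% | 5.1% |
| Middle | 25% vs 15% | 0.5 SD = 0.21 | 0.10 × 0.21 = 0.021 | 13% | 6.6% |
| High | 30% vs 10% | 1 SD = 0.42 | 0.20 × 0.42 = 0.084 | 53% | 31% |

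Equal refusal does not remove the problem. With 10% refusal in both arms and gaps that differ by 0.25 SD, the bias is 0.10 × 0.105 = 0.0105, or 7% of 0.16.

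**A second model.** Suppose that consent depends on the change score in one arm only, through a threshold on a correlated normal variable. The shift is 0.42 × ρ × φ(z_c)/c, where c is the consent rate, z_c its normal quantile, φ the normal density and ρ the correlation.

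- c = 0.90, ρ = 0.1: 0.42 × 0.1 × 0.1755/0.90 = 0.008, 5% of 0.16.
- c = 0.70, ρ = 0.5: 0.42 × 0.5 × 0.3477/0.70 = 0.104, 65% of 0.16.

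Both models say the same: negligible under mild selection, serious under strong selection. The documents do not show which applies.

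**The case against.** The best case against is that consent before allocation is the natural joint reading. Participants are enrolled and then allocated. Students hear about randomisation within a consent procedure. The Limitations section treats consent as a recruitment risk, and the sample size separates an enrolment target of 275 from a 20% drop-out. The questionnaire descriptions are also not exhaustive: neither mentions the participant's name, though the plan says just afterwards that each questionnaire asks for it. A missing consent item at baseline is therefore weak evidence that there is none. Information sheets that might settle the point are not in the text available here.

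That makes earlier consent plausible, and this review does not claim otherwise. But none of those passages gives a date, and none cancels the late request.

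It can also be said that a student put off by either activity may simply not return the final questionnaire, so moving consent helps only with those who open it and refuse. That stands: earlier consent closes one route of selection, not all of them.

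The magnitudes do rest on assumptions throughout. The low and middle cases barely move the error rate. The middle and high cases average 20% refusal, which alone uses up the plan's drop-out allowance. The missing analysis set is a gap whenever consent is taken; it matters here because nothing else in the plan fixes how the compared groups are formed.

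**Conclusion.** The concern holds as a conditional statement: as written, the plan lets a choice made after exposure decide whether a randomised student enters the primary comparison. The text establishes that much, and it also establishes that no single consent date is given. It does not establish that bias will occur. With the plan's SD of 0.42 and 110 per arm, plausible to extreme assumptions about refusal give a bias of 0.005 to 0.084 in either direction, against a planned difference of 0.16. The figures rest on assumed refusal rates and gaps, and on 110 analysed students per arm. The change is worth making because it is cheap and loss of this kind is hard to repair later. Confidence is medium.

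**What to change.** - Reconcile the Data collection, Blinding procedures and Ethics sections, and state one time for student consent.
- Take consent, including data use, in the start-of-year questionnaire before randomisation, using the high-level description already planned, so that it need not reveal which activity is the sham. If baseline is already collected (the protocol is dated 19 October 2018 and does not say), take it before the arm-specific materials are sent ahead of the final visit.
- Do not make inclusion depend on a second agreement at the end, beyond the right to withdraw.
- In the Statistical analysis section, state that all consenting students with an outcome are analysed by randomised arm. Use the self-reported activity item only to describe adherence and for a supportive analysis.
- Report consent, withdrawal and questionnaire completion by arm.

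The cost is one survey item moved, or one short consent e-mail, plus two sentences of analysis text. The small downside is that students who decline are lost before randomisation. Loss from activities not done or final questionnaires not returned remains and needs its own reporting.

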We have only identified one study that assessed the effect of an intervention on students' levels of patient-centredness. In this uncontrolled UK study, first-year dental undergraduates were given an attitudinal questionnaire to complete before and after their behavioural science course. No significant difference was found between their mean pre- and post-course PPOS scores (pre-course mean scores: 3.44 SD 0.33; post-course mean score: 3.37, SD 0.19; $P > 0.05$). We have found no controlled trials that test the effect of interventions on medical students' levels of patient-centredness, and no trials that look at the effect of early patient contact in the form of an unaccompanied visit to a patient in their home.

Aim of the study

The aim of this study is to assess how a structured, in-depth, home-based interview with a patient with a chronic illness affects first-year medical students' patient-centredness.

A nested study will assess whether the GP's level of patient/doctor-centredness affects changes in their student's level over the year.

Methods

Study setting

The study will take place in the Berner Institut für Hausarztmedizin (BIHAM) at the University of Bern, Switzerland, and a subset of the >700 General Practitioner (GP) teaching practices that are affiliated to it.

Study participants

The population will be medical students who are in the first year of their studies (their first Bachelor year) at the University of Bern, during their longitudinal placements in primary care. The GP teachers are family doctors that are accredited by BIHAM to take medical students.

Study design

This will be a randomised controlled trial. During their first Bachelor year, each medical student will spend a series of six half-days at the practice of a GP teacher that she/he has been allocated to. Students will be randomly assigned to either the intervention or the sham comparator which will take place during their last half-day in their practices. All students will complete an on-line version of the PPOS-D12 questionnaire at the start of the academic year and once more after the last half-day at their GP teachers' practices.

Intervention

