At the end of their students' attachments, their GP teachers will complete a SurveyMonkey questionnaire that asks them to complete the PPOS D12 form. Consent to use these data for research will also be requested.

Each of these questionnaires will ask for the participant's name, so that pre-intervention, post-intervention, and GP's data can be linked and compared.

Outcome measures

The primary outcome measure will be the change in students' PPOS-D12 scores from baseline (at the start of the academic year) to the end of their year-long primary care attachment.

Secondary outcomes will be the effect of students' gender, previous experience and prior exposure to chronic illness in the participant or her/his close relatives and friends on their PPOS-D12 scores

A nested study will measure the strength of association between the GP teachers' own levels of patient/doctor-centredness and changes in their students' levels over the year.

Development of the intervention

Following a literature review and discussion, RF, [name] and MH developed a patient interview pro-forma which was designed to identify patients' views on their illnesses, how it affects their lives in physical, psychological and social terms, and how their relationships with their GPs impacts on their lives. The sections of the interview pro-forma map across to Mead and Bower's conceptual framework of patient-centredness given above [22].

Six medical students who had been visiting their GP teachers for eight half-days per year since their first year of study agreed to pilot the intervention in November 2017. The GP teachers were asked to select a patient with a chronic illness for their students, and to organise 2.5-hour interviews, half of the students at the patients' home and in the other half in the teaching practices. Students were asked to use the questionnaire pro-forma. In addition, the students each had a 30-minute interview with a practice nurse to assess their perceptions of the effect of the illnesses on their patients, and finally a one-hour discussion with their GP teacher to reflect on their encounters with the patients, discuss their findings, and talk about any difficulties that may have arisen.

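### The nested study asks whether the GP's attitude affects the student's change, but the GP's only PPOS-D12 score is taken at the end of the attachment, so time order is not established

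*Combined protocol and SAP*

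**What the plan says.** Under Aim of the study the nested question is directional: "A nested study will assess whether the GP's level of patient/doctor-centredness affects changes in their student's level over the year". Under Outcome measures it is associational: "A nested study will measure the strength of association between the GP teachers' own levels of patient/doctor-centredness and changes in their students' levels". The Abstract uses the same associational wording.

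The GP is measured once. Data collection says that, when the students' attachments end, "their GP teachers will complete a SurveyMonkey questionnaire that asks them to complete the PPOS D12 form". GP consent to research use is requested at the same point. No GP questionnaire at the start of the year is described. For students there is one: "At the start of the academic year (i.e. before the interventions), students will complete a SurveyMonkey questionnaire".

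Study design places the arm-specific activity at the very end: "Students will be randomly assigned to either the intervention or the sham comparator which will take place during their last half-day in their practices". The GP takes part in both arms. The intervention sequence closes with the practice nurse interview and "then a structured debriefing interview with the GP teacher". In the sham arm the student discusses the document's questions with the GP. The two Development sections add that each arm's material goes to the GP before the final visit.

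Statistical analysis plans paired t tests for the nested study and does not mention arm. The plan does not state that GP attitude is assumed stable, and Limitations does not mention the timing.

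**The concern.** The GP's attitude is the exposure in the nested study and the student's change is the outcome. The exposure is recorded only after the outcome period has ended. Three things could then shape the GP score or its availability:

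- the student, over the series of half-days (reverse influence);
- the arm, because the GP has just debriefed a patient interview or discussed a communication-skills text, and both concern how doctors relate to patients;
- selective response, because the GP decides whether to answer and consent after knowing which activity took place.

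At stake is how a nested result may be read. A positive association might be reported as the GP's influence on the student when the data do not fix its direction. The randomised comparison of students is not involved.

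**Working it through.** The plan gives no sample size, power or target correlation for the nested study, so there is no figure of its own to reproduce. The checks below are sensitivity calculations.

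**Inputs from the protocol.** Assumed arm difference in student change 0.16, SD 0.42, equal allocation, 220 evaluable students (Statistical analysis). PPOS in resident physicians over one year: SD 0.48 at start, 0.51 at end, SD of change 0.42 (Background).

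**Assumptions.** GP score SD 0.5 (0.48 in the variants); one student per GP; all 220 pairs complete. The shift in GP score by arm (d) and the GP's response to student change (b) are not in the documents and are varied.

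**1. Time order.** Student baseline: start of year. Arm-specific activity with the GP: last half-day. Student follow-up: after the last half-day. GP score: end of attachment. Nothing about the GP's attitude is recorded before the student's change.

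**2. Correlation induced by arm alone, with no GP effect.** A 1:1 arm indicator has variance 0.5 × 0.5 = 0.25, so

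r = 0.25 × 0.16 × d / (0.42 × 0.5)

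- d = 0.1: 0.004 / 0.21 = 0.019
- d = 0.2: 0.008 / 0.21 = 0.038
- d = 0.3: 0.012 / 0.21 = 0.057

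With a within-arm GP SD of 0.48, and the between-arm part added to both variances, d = 0.05 gives 0.01, d = 0.3 gives 0.06 and d = 0.5 gives 0.09.

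For scale, the two-sided 5% critical correlation at n = 220 is tanh(1.96 / √217) = 0.13. Every value above is below it. Adjusting for arm removes this shift.

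**3. Correlation induced by reverse influence, with no GP effect.** If the GP score moves by b per point of student change,

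r = 0.42b / √(0.48² + 0.42²b²)

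- b = 0.05: 0.04
- b = 0.1: 0.09
- b = 0.2: 0.084 / 0.487 = 0.17
- b = 0.3: 0.126 / 0.496 = 0.25

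The last two exceed 0.13. Adjusting for arm does not remove them.

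**4. How good a proxy is an end-of-year score?** The resident figures imply a start-to-end correlation of

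(0.48² + 0.51² − 0.42²) / (2 × 0.48 × 0.51) = 0.3141 / 0.4896 = 0.64

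If GPs behaved the same way (an assumption), a true correlation of 0.20 between the starting GP score and student change would appear as about 0.64 × 0.20 = 0.13. The late score is informative but diluted. Established GPs may be more stable than residents; the documents do not say.

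**The case against.** **The outcome is already an association.** The Abstract and Outcome measures both say so, and an end-of-year score can estimate one. This stands and limits the point. What remains is the directional aim, which the timing does not support, and an unstated stability assumption.

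**An earlier score would not prove influence either.** Correct. Students are allocated to GPs, but random allocation to GPs is not stated. An early score would establish time order, which is necessary for the stated aim but not sufficient.

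**Late measurement protects blinding.** GPs are meant to have only a general description of the objectives, and the items in Appendix 1 would show them the construct before they lead the debriefing or discussion. The protocol does not give this as its reason. Students see the same form at the start of the year and are still treated as blinded; the information withheld is which activity is the sham, and the items do not reveal that. GPs do help deliver both activities, however, so mild priming is a real if modest downside.

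**Arm adjustment has nowhere to go.** As the plan is written, this is right: a paired t test has no place for an arm term. It also compares the means of two unlike quantities, a level and a change, and so does not measure association at any measurement time. The remedy therefore has to name a different analysis.

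**Conclusion.** The point holds as a mismatch between aim and timing. The only GP score follows both the student's change and the GP's own part in the arm-specific activity, so direction is not established. Influence of the student on the GP and arm-dependent GP response cannot be excluded.

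A reader might infer that the nested study can show nothing, or that the arm-specific debriefing seriously confounds it. The documents do not support either reading. The defined outcome is an association, which a late score can estimate if GP attitude is reasonably stable. Both arms include a discussion with the GP, and no figure in the plan suggests that arm shifts GP scores much. Under assumed shifts of 0.1 to 0.3 the induced correlation is only about 0.02 to 0.06.

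Reverse influence is potentially larger, 0.04 to 0.25 over the slopes tried, but those slopes are pure assumption. The size of selective response cannot be estimated from the documents. This is a minor, worthwhile improvement to a secondary component; the primary comparison is untouched.

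**What to change.** 1. Send the existing GP PPOS-D12 form, with its consent request, at the start of the academic year alongside the student baseline and before any arm-specific material. Sending it just before the last half-day would remove only the arm channel, because the student could already have influenced the GP during the earlier visits.
2. Replace the paired t test for the nested study with a regression of student change on GP score, with allocated arm as a covariate. Report the slope with its confidence interval.
3. If the timing cannot be moved, keep the arm-adjusted regression, bring the wording under Aim of the study into line with the association in Outcome measures, and state under Limitations that GP attitude is assumed stable over the year. The arm term removes a shift in GP scores by arm; it does not remove reverse influence or fully deal with selective response.

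Cost: one survey e-mail sent earlier, with the same form and no extra items. Downside: GPs see the measured construct sooner, so mild priming is possible in both arms, though it arises before allocation-specific material is sent. Even with the earlier score, the report should claim time order and not causation.
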